## **6.7 BASELINE, TIME WINDOWS AND CALCULATED VISITS**

For efficacy endpoints, baseline is defined as the pre-treatment observation at Visit 2. If Visit 2 is missing, then Visit 1 will be used for baseline.

For laboratory safety measurements, the last measurements taken prior to the treatment start will be considered as baseline.

The visit schedule with accompanying details can be found in Flow Chart 1 in CTP. Measurements taken after start of treatment will be considered either on- or off-treatment values based on definition in Table 6.1: 1.

## 7. PLANNED ANALYSIS

Descriptive statistics for continuous variables will be N (number of patients with non-missing values), mean, standard deviation (SD), minimum, median, and maximum. In general, means, SDs, will be presented to one more decimal place than the raw data. Minimums and maximums will be presented to the same number of decimal places as the raw data.

Tabulations of frequencies for categorical data will include all possible categories and will display the number of observations in a category as well as the percentage(%) relative to the respective treatment group. Percentages will be rounded to one decimal place. The category "missing" will be displayed only if there are actually missing values. Percentages will be based on all patients in the respective patient set no matter whether they have non-missing values or not.

### 7.1 DEMOGRAPHIC AND OTHER BASELINE CHARACTERISTICS

Only descriptive statistics are planned for this section of the report. Demographic parameters collected and to be presented include, but are not limited to, the following:

- Sex (Male, Female)
- Race and ethnicity (as defined in the eCRF)
- Region
- Age [years]
- Height [cm]
- Weight [kg] (continuous)
- Body mass index [kg/m^2] (defined as weight [kg]/(height [cm]/ 100))
- Smoking history (Never-smoked, Former-smoker, Currently smokes)
- Alcohol History (Never drink, Former-drinker, Currently drinker)
- COVID-19 Symptom
- SARS-CoV-2 Seropositive at baseline
- WHO clinical progression scale at baseline
- Clinical Frailty Scale
- Blood type
- Cardiac disease disease (Yes, No)
- Hypertension (Yes, No)
- Respiratory disease (Yes, no)
- Diabetes mellitus (Yes, No)
- Kidney disease (Yes, No)
- Coagulation parameters (Normal, Abnormal)
- Infection date to admission (< 7 days, 7 days)

- Time to drug intake from hospitalization(< 24 hours, 24 hours)
- Duration of symptoms before hospitalization

## **7.2 CONCOMITANT DISEASES AND MEDICATION**

Concomitant diseases will be summarised descriptively. The frequency [N (%)] of patients with different concomitant diseases (baseline conditions) will be presented. The concomitant medications taken at baseline and those taken while on treatment will be coded using the World Health Organization (WHO) Drug coding dictionary. These will then be summarized by standardized drug grouping and listed by patient with each medication taken.

Concomitant non-Drug Therapies will also be summarized descriptively.

## **7.3 TREATMENT COMPLIANCE**

This section is not applicable because study medication is not dispensed directly to patients and instead is administered to hospitalized patients by a site staff member. Any missed doses are recorded in the eCRFs.

## **7.4 PRIMARY ENDPOINTS**

### **7.4.1 Primary Analysis**

The primary objective is to evaluate the difference in proportions of patients alive and free of mechanical ventilation at Day 29 with BI 764198 and placebo. The primary analysis of the primary efficacy endpoint will be performed on the full analysis set (FAS) following the treatment policy, i.e., patients who initiate other therapies during the treatment period or patients who terminate the study medication prematurely will be followed up for data collection until the time point of interest and all these data will be included in the analysis.

A logistic regression model will be used including covariates of treatment, WHO clinical progression scale at baseline, age, creatinine at baseline, and duration of symptoms before hospitalization. The point estimate, standard error and confidence interval for the risk difference in proportions will be derived based on the estimates from the logistic regression model. The fitted logistic regression model will be used to predict the probability of response for every subject in the study as if they had received treatment or placebo, and the average in the difference of response probabilities between treatment and placebo will be calculated. For primary analysis, nominal p-value for the risk difference will be provided.

Proprietary confidential information © 2021 Boehringer Ingelheim International GmbH or one or more of its affiliated companies

With a data set of  $n$  subjects, define a binary response vector for  $n$  patients alive and free of mechanical ventilation at Day 29 as  $Y = (y_1, y_2, \dots, y_n)^T$ , and covariate matrix  $X = [x_1, x_2, \dots, x_n]^T$ , where  $x_i$  indicates a covariate vector that consists of treatment, severity grade at baseline, age, creatinine at baseline, and duration of symptoms before hospitalization for  $i$ th subject. A logistic regression model assumes  $\log \frac{P(y_i=1|x_i)}{1-P(y_i=1|x_i)} = \beta^T x_i$ . Define  $\beta$  as the maximum likelihood estimate of  $\beta$ , and its estimated variance-covariance matrix is  $V$ . To estimate the proportions of responders in both treatment and placebo arms, and their difference:

1. Create the new covariate matrix  $X_t$  from  $X$  by adjusting the column corresponding to treatment assignment such that all subjects are in the treatment group. Then calculate the vector of estimated probabilities of response to treatment,  $\hat{P}_t$ , from  $X_t$  and  $\beta$ :  $\hat{P}_t = \text{logit-1}(X_t \beta)$ .
2. Similarly, assume each subject is assigned to placebo and repeat the step 1 to get  $X_c$  and  $\hat{P}_c$  for placebo group.
3. The estimated difference in proportions is  $d = \frac{\hat{P}_t - \hat{P}_c}{n}$ , where  $\hat{P}_{ti}$  and  $\hat{P}_{ci}$  are the  $i$ th elements of  $\hat{P}_t$  and  $\hat{P}_c$ , respectively. Define  $A_t$  as a vector with elements  $A_{ti} = \hat{P}_{ti}(1 - \hat{P}_{ti})$  and  $A_{ci} = \hat{P}_{ci}(1 - \hat{P}_{ci})$ . Then, the standard errors of these estimators are derived as follows:

$$d_t = \frac{A_t' X_t}{n}$$

$$d_c = \frac{A_c' X_c}{n}$$

$$SE(d) = \sqrt{d_t V d_t' + d_c V d_c' - 2 d_c V d_t'}$$

The confidence interval of the estimation is  $d \pm Z_{1-\alpha/2} \cdot SE(d)$ . The details of logistic regression analysis and SAS code are provided in [Section 10.1.1](#) and Ge, et al. (2011) ffi

In addition to the primary analysis, an analysis using composite strategy will be conducted to handle intercurrent events. The expected intercurrent events of interest in this trial are treatment discontinuation, death, and use of new therapies which are SoC for COVID-19 including Remdesivir and Dexamethasone. This analysis strategy considers patients with intercurrent events as treatment failure.

Sensitivity analyses will be conducted on the primary endpoint as follows:

- A logistic regression model including covariates of treatment, severity grade at baseline, age, creatinine at baseline, D-dimer at baseline, and duration of symptoms before hospitalisation in FAS.

- A logistic regression model including covariates of treatment, severity grade at baseline, age, creatinine at baseline, and time from first symptoms to start medication in FAS.
- A logistic regression model including covariates of treatment, severity grade at baseline, age, creatinine at baseline, and time from screening of patient to first drug in mouth in FAS.
- A logistic regression model including covariates of treatment, severity grade at baseline, age, creatinine at baseline, and time from hospitalization to first drug in FAS.
- A logistic regression model including covariates of treatment, severity grade at baseline, age, creatinine at baseline, and duration of symptoms before hospitalization on PPS. This analysis will be performed only if number of patients with IPDs excluded from PPS is greater than 10% of total number of randomised patients.
- A Cochran-Mantel-Haenszel type weighted average of differences with weights by severity grade at baseline on FAS. The details of Cochran-Mantel-Haenszel test and SAS code are provided in [Section 10.1.2](#).
- To deal with patients who stop treatment due to sponsor's request, a logistic regression model including covariates of treatment, severity grade at baseline, age, creatinine at baseline, and duration of symptoms before hospitalization by defining a hypothetical estimand: treating these patients as non-responders (i.e. neither alive nor free of mechanical ventilation).
- A logistic regression model including covariates of treatment, severity grade at baseline, and age in FAS

#### **7.4.2 Subgroup analysis**

Analyses for subgroups specified in [Section 6.4](#) will be performed for the primary endpoint using the logistic regression model to evaluate treatment-by-subgroup interactions.

### **7.5 SECONDARY ENDPOINTS**

#### **7.5.1 Key secondary endpoints**

[figure not shown]
This section is not applicable as no key secondary endpoint has been specified in the protocol.

[figure not shown]
#### **7.5.2 (Other) Secondary endpoints**

Secondary endpoints will be analyzed on the FAS using treatment policy estimand.

Proprietary confidential information © 2021 Boehringer Ingelheim International GmbH or one or more of its affiliated companies

- Analysis of patients alive and discharged free of oxygen at Day 29 will be conducted using the same model as for the primary endpoint, to assess the difference in proportions of patients with BI 764198 and placebo.
- Analysis of patients with occurrence of any component of composite: In-hospital mortality or intensive care unit (ICU) admission or mechanical ventilation at Day 29, will be conducted using the same model used as the primary endpoint, to assess the difference in proportions of patients with BI 764198 and placebo.
- Time to response, defined as clinical improvement of at least 2 points (from randomisation) on the World Health Organization Clinical Progression Scale, discharge from the hospital, or considered fit for discharge (a score of 0, 1, 2, or 3 on the Clinical Progression Scale), whichever comes first, by Day 29, will be analysed using the Cox proportional-hazards model adjusting for treatment, age, creatinine at baseline, and duration of symptoms before hospitalisation. Hazard ratio and Kaplan-Meier curves with 95% confidence interval will be provided. Patients who do not respond will be censored at Day 29. Patients who prematurely discontinued from the treatment or lost to follow-up will be censored at the time of their last observed assessment. Patients who die prior to observing response will be censored at Day 29.
- The number of ventilator free days will be analysed using an ANCOVA model including treatment, age, creatinine at baseline, and duration of symptoms before hospitalisation. WHO progression scale below 7 are defined as ventilator free. Hence, ventilator free days can be counted as number of days with WHO progression scale below 7 from the day of randomization to day 29. A sensitivity analysis excluding patients who died during treatment period will be conducted.
- Analysis of mortality at Day 15, 29, 60 and 90 will be conducted using the same model as for the primary endpoint, to assess the difference in proportions of patients with BI 764198 and placebo.

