2.1.3 Secondary endpoints

- Patients alive and discharged free of oxygen at Day 29
- Patients with occurrence of any component of composite: In-hospital mortality or intensive care unit (ICU) admission or mechanical ventilation at Day 29
- Time to response, defined as clinical improvement of at least 2 points (from randomisation) on the World Health Organization Clinical Progression Scale, discharge from the hospital, or considered fit for discharge (a score of 0, 1, 2, or 3 on the Clinical Progression Scale), whichever comes first, by Day 29

World Health Organization (WHO) Clinical Progression Scale [R20-2002]:

0. Uninfected; no viral RNA detected
1. Asymptomatic; viral RNA detected
2. Symptomatic; independent
3. Symptomatic; assistance needed
4. Hospitalised; no oxygen therapy
5. Hospitalised; oxygen by mask or nasal prongs
6. Hospitalised; oxygen by non-invasive ventilation or high flow
7. Intubation and mechanical ventilation, $pO_2/FiO_2 \geq 150$ or $SpO_2/FiO_2 \geq 200$
8. Mechanical ventilation $pO_2/FiO_2 < 150$ ($SpO_2/FiO_2 < 200$) or vasopressors
9. Mechanical ventilation $pO_2/FiO_2 < 150$ and vasopressors, dialysis, or extracorporeal membrane oxygenation (ECMO)
10. Death

- Number of ventilator free days by Day 29
- Mortality at Day 15, 29, 60, and 90

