5. ASSESSMENTS

5.1 ASSESSMENT OF EFFICACY

5.1.1 Proportion of patients alive and free of mechanical ventilation at Day 29

Patients who are alive and free of mechanical ventilation at Day 29 is defined as those who have not died at Day 29 and those who do not depend on mechanical ventilation for breathing at Day 29.

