5.1.3 Other efficacy assessments

The duration of, and time to, ICU admission, the number of ventilator-free and oxygen-free days, the initiation of new ventilation use, and duration of hospitalisation will be derived from source documents. The date of discharge from hospital and/or death will be recorded on the eCRF.

The Clinical Frailty Scale (CFS) [[R20-2080](#)] will be determined at the time point indicated on the [Flow Chart](#). The CFS is a means of summarising the overall level of fitness or frailty of an individual. It comprises a 9-point scale with categories ranging from 1 (very fit) to 9 (terminally ill).

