6.2.2 Treatment period(s)

The treatment period starts with Visit 2 (Day 1, randomization) and ends with the EOT visit (possible Day 2 through Day 29). Patients will remain hospitalised during the treatment period and daily protocol visits will be conducted to complete procedures according the [Flow Chart](#). Patients may receive treatment with study drug for up to 28 days, however if a patient is well enough to be discharged, then study drug may be stopped before the maximum treatment duration (i.e. 28 days).

EOT visit should be completed the day after the last dose of study drug is administered for all patients regardless of discharge status. EOT visit is expected to align with day of discharge, unless it is planned for a patient to remain hospitalised after treatment with study drug is stopped. EOT visit should occur no later than Day 29.

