6.2.3 Follow-up period and trial completion

For all randomised patients, termination of trial medication and trial completion must be recorded on the corresponding eCRFs.

Applicable FUP visits and EOS visits will be conducted remotely by a phone contact for all patients that have completed treatment, EOT visit, and discharge. Each of these visits includes vital status.

FUP visits should be conducted as follows:

- FUP 1 should be performed 4 days after EOT visit for all patients.
- FUP 2 and FUP 3 which correspond to study Day 15 and Day 29 after start of therapy, should be performed *if the time point is applicable after drug discontinuation*. FUP 2 and FUP 3 visits should not be conducted within +/- 2 days of EOT or FUP 1.
- FUP 4 and EOS which correspond to study Day 60 and Day 90 will be performed for all patients.

If a patient remains hospitalized after EOT visit, applicable FUP visits and the EOS visit will be conducted in hospital until discharge and thereafter by telephone.

If a patient withdraws participation from the study, it may be agreed to collect vital status per the remaining originally planned visit schedule according to the [Flow Chart](#).

Trial completion is defined as patients completing the FUP and EOS visits according to the [Flow Chart](#).

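### The secondary composite counts only in-hospital deaths, so an out-of-hospital death before Day 29 with no earlier ICU or ventilation event is scored event-free

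*SAP*

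**What the plan says.** Protocol 2.1.3 lists as a secondary endpoint "Patients with occurrence of any component of composite: In-hospital mortality or intensive care unit (ICU) admission or mechanical ventilation at Day 29". The protocol synopsis names the same three components, and so does SAP 7.5.2: "In-hospital mortality or intensive care unit (ICU) admission or mechanical ventilation at Day 29". The SAP says the analysis "will be conducted using the same model used as the primary endpoint": a covariate-adjusted difference in proportions on the Full Analysis Set. No visible text in either document extends the death component beyond the hospital.

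The other endpoints that involve death have no such limit. Protocol 5.1.1 defines success on the primary endpoint partly through "those who have not died at Day 29", with no mention of place. SAP 7.5.2 adds a separate mortality endpoint, also without restriction on place: "Analysis of mortality at Day 15, 29, 60 and 90 will be conducted using the same model as for the primary endpoint".

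Patients can leave hospital well before Day 29. Protocol 6.2.2 says that "if a patient is well enough to be discharged, then study drug may be stopped before the maximum treatment duration". On follow-up and end-of-study contacts, protocol 6.2.3 says "Each of these visits includes vital status", and protocol 5.1.3 says "The date of discharge from hospital and/or death will be recorded on the eCRF".

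**The concern.** The three components are meant to mark deterioration, and death is the worst of them. Limiting it to the hospital stay makes the observation window for death end at discharge, or at least pause until a readmission. The ICU and ventilation components lose little by this, because they cannot occur at home. Death can.

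Discharge is not a baseline feature. It happens after randomisation, it is one route to response in protocol 2.1.3, and protocol 5.1.3 derives duration of hospitalisation as an efficacy assessment. If treatment changes when patients go home, it changes how long each arm is at risk of a countable death. An arm with earlier discharge could then show a lower composite rate without any death having been prevented. The same patient can also be a failure on the primary endpoint and event-free on the composite for no reason other than where the death took place.

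**Working it through.** The documents give no event rate, effect size or power for the composite, so there is no figure to reproduce. The check is a comparison of definitions, followed by two short calculations.

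**1. One patient, three endpoints.** Take a patient discharged without ICU admission or mechanical ventilation who dies at home on Day 25.

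| Endpoint | Source | Result |
|---|---|---|
| Alive and free of mechanical ventilation at Day 29 | Protocol 5.1.1 | Failure |
| Mortality at Day 29 | SAP 7.5.2 | Death |
| Composite | Protocol 2.1.3, SAP 7.5.2 | No event |

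Had this patient still been on a ward on Day 25, the composite would have recorded an event. Only the place of death differs.

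**2. Effect of each such death.** Planned size is 65 per arm, 130 in total (protocol synopsis). Reclassifying k deaths in one arm moves that arm's crude rate by k/65:

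- k = 1: 1/65 = 1.54 percentage points
- k = 2: 2/65 = 3.08 percentage points
- k = 3: 3/65 = 4.62 percentage points

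As an illustration only, assume composite rates of 40% on placebo and 25% on active, a difference of 15.0 points. One added death on placebo alone gives 16.5; one on active alone gives 13.5; one in each arm leaves 15.0. The model-adjusted difference would move by a similar but not identical amount.

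**3. How many such deaths.** The documents do not say. If 0.5% to 2% of patients were affected (an assumption), that is 130 × 0.005 = 0.65 to 130 × 0.02 = 2.6 patients over both arms.

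**4. Can Day 29 vital status be obtained?** Under protocol 6.2.3, FUP 1 is at EOT + 4 days, and the Day 29 contact (FUP 3) is not made within 2 days of EOT or FUP 1. On nominal days:

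- EOT on Day 22 or earlier: FUP 1 is on Day 26 or earlier, at least 3 days before Day 29, so FUP 3 applies.
- EOT on Day 23 or 24: FUP 1 is on Day 27 or 28, so FUP 3 is omitted. The +2 window for FUP 1 reaches Day 29 or 30, but otherwise the next planned contact is Day 60.
- EOT on Days 25 to 29: FUP 3 is omitted, but FUP 1 falls on Days 29 to 33 and so covers Day 29.

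Day 60 and Day 90 contacts are planned for all patients and the date of death is recorded. Status at Day 29 can therefore be derived, in part retrospectively, for nearly all patients who remain in follow-up.

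**5. Imputation.** SAP 6.6 sets the WHO score to 10 at remaining visits for any death before Day 29. For ventilator-free days, SAP 7.5.2 treats only scores below 7 as ventilator-free. If the composite's ventilation component were derived from the imputed scores in the same way, the patient in step 1 would count after all. The SAP does not say whether it is.

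**The case against.** The best defence is that nothing is inconsistent and no death disappears. The definition agrees across synopsis, protocol and SAP. It can be read as a deliberate measure of deterioration in hospital. Deaths at any location by Day 29 enter the primary endpoint and the mortality endpoint, so a reader would see earlier discharge with unchanged mortality in the same report. Composites routinely disagree with a primary endpoint for some patients; ICU admission alone has that effect here. The affected group is also narrow: exclusion criteria 8 and 9 in protocol 3.3.3 remove patients expected to move to another care facility and those not committed to full support. Finally, parts of both documents are not public, so a supportive all-cause version may already exist there.

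Most of this stands, and it keeps the point small. It does not remove the dependence of the composite itself on discharge timing, and the separate mortality analysis does not correct the composite rate.

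Four stronger readings are tempting, and the documents do not support them:

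- *Every patient who dies after discharge is scored event-free.* Any one component is enough, so an earlier ICU or ventilation event may already count (the phrase about Day 29 leaves unclear whether events up to that day qualify). A death in hospital after readmission also fits the wording.
- *Vital status is collected at Day 29 for everyone.* FUP 3 is conditional, and after withdrawal from the study vital status is collected only if agreed (protocol 6.2.3).
- *The composite is biased in favour of the drug.* The stated objective concerns risk or severity of ARDS. Nothing in the documents shows that treatment shortens stay or that out-of-hospital deaths would differ between arms.
- *Such deaths are treated as the best outcome.* The composite is binary and ranks nothing.

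**Conclusion.** The point holds in a limited form. As written, a death outside hospital before Day 29, in a patient with no earlier ICU admission or mechanical ventilation, is a non-event on the composite, although it counts in the primary endpoint and in Day 29 mortality. Capture of deaths therefore depends on a post-randomisation outcome that treatment may affect.

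The size is probably small: 1.5 percentage points of one arm's crude rate per such death, and no change in the difference if equal numbers occur in two arms of 65. The number of deaths is an assumption, not a document figure. The endpoint is secondary, and protocol 7.1 plans no formal testing. This is an inexpensive improvement to the SAP; it does not threaten the trial's main conclusion. It rests on the literal wording and on the SAP 6.6 imputation not feeding the composite, which the SAP leaves open.

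**What to change.** Keep the protocol wording of the composite. In SAP 7.5.2:

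1. Add a supportive version in which the death component is death from any cause by Day 29, in or out of hospital, derived from follow-up vital status and date of death. Analyse it with the same model and report both versions side by side.
2. State whether the SAP 6.6 imputation of WHO score 10 after death is used when deriving the composite.

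Both are best settled before treatment information is released. No new data are needed for patients who remain in follow-up; those who withdraw without agreeing to vital status collection may still lack a Day 29 status. The cost is one additional supportive analysis of a secondary endpoint.

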## **6.6 HANDLING OF MISSING DATA AND OUTLIERS**

All patients will be followed to collect necessary efficacy and safety information, even if patients discontinue study medication prematurely.

For patients who miss WHO clinical progression scales, imputation will be performed using data from other sources if available, e.g., oxygen use, ventilation use, etc.

For patients who miss start date and/or end date of hospitalisation, ventilator use and oxygen use, data will be imputed based on available information on the eCRF page of WHO Clinical Progression Scales.

Proprietary confidential information © 2021 Boehringer Ingelheim International GmbH or one or more of its affiliated companies

If a patient dies while hospitalised, the number of days of hospitalisation will be imputed until day 29 (i.e. 28 days of hospitalisation). If a patient dies while in ICU, the duration of ICU stay will be imputed until day 29. For patients who die before day 29, WHO progression scale will be imputed as 10 for all remaining visits: in addition, duration of oxygen (or ventilation) use will be imputed until day 29.

For patients who are discharged before day 29, WHO progression scale will be imputed using the last available observation if no additional data is available after discharge.

For patients who discontinue treatment early, if the patient is on oxygen/ventilation before discontinuation, the number of days on oxygen/ventilation will be imputed until day 29. If the patient is not on mechanical ventilator at the last observed assessment, the number of ventilator free days will be imputed until day 29.

For missing or incomplete AE dates, BI internal procedures and guidelines will be followed Q2J1. The same philosophy will be applied to missing concomitant medication dates (where applicable), and dates of study medication discontinuation, and trial completion date.

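### SAP rules for patients who stop drug early do not fit the treatment-policy estimand declared for secondary endpoints: Section 6.6 allows opposite ventilator-free-day values, and Section 7.5.2 lists drug stop as a censoring trigger

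*SAP*

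**What the plan says.** **Estimand.** SAP 7.5.2 opens with "Secondary endpoints will be analyzed on the FAS using treatment policy estimand". SAP 7.4.1 shows what the term means in this trial: patients who stop drug early or start other therapies "will be followed up for data collection until the time point of interest and all these data will be included in the analysis".

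**Imputation, SAP 6.6.** Two consecutive sentences deal with patients who discontinue treatment early.
- Sentence 1: "if the patient is on oxygen/ventilation before discontinuation, the number of days on oxygen/ventilation will be imputed until day 29".
- Sentence 2: "If the patient is not on mechanical ventilator at the last observed assessment, the number of ventilator free days will be imputed until day 29".

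The rule just before them, for patients discharged before Day 29, carries an explicit limit: "WHO progression scale will be imputed using the last available observation if no additional data is available after discharge". Deaths have their own rule: "For patients who die before day 29, WHO progression scale will be imputed as 10 for all remaining visits".

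**Time to response, SAP 7.5.2.** Non-responders are censored at Day 29. Then: "Patients who prematurely discontinued from the treatment or lost to follow-up will be censored at the time of their last observed assessment". For deaths: "Patients who die prior to observing response will be censored at Day 29". Protocol 7.2.3 gives only the Day 29 rule for non-responders, and SAP Section 4 records no change to the planned analysis.

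**Data available.** Footnote f of the protocol Flow Chart has ventilation and oxygen parameters collected daily to Day 29 in patients who stop treatment and are not discharged. It asks for the WHO score at Day 29. SAP 7.5.2 counts a day as ventilator-free when the WHO score is below 7, from randomisation to Day 29.

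**The concern.** Under treatment policy, what happens after drug stop belongs to the outcome. Two rules instead treat drug stop as the point where observation may end.

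In SAP 6.6, sentence 1 takes its anchor from before drug stop and does not say that later days must be missing, although footnote f supplies those days for patients still in hospital. Sentence 2 takes its anchor from the last observed assessment. A patient ventilated before drug stop and later seen off the ventilator meets both conditions, and the sentences send the same days in opposite directions.

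In SAP 7.5.2, drug stop stands beside loss to follow-up as a reason to censor, and the text does not say which assessment counts as the last. Footnote f schedules the WHO score after drug stop at Day 29 but oxygen and ventilation daily. A patient without a Day 29 score could therefore have a last WHO assessment close to drug stop although later respiratory data exist.

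At stake are reproducible ventilator-free days and, under one reading, recorded responses left out of the hazard ratio.

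**Working it through.** The plan states no figure on this point, so there is none to reproduce. The check has two parts.

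**1. Ventilator-free days (SAP 6.6 with 7.5.2)**

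Count = days from 1 to 29 not spent on the ventilator, assuming that the 6.6 rules feed this count. Dropping Day 1 would lower every count by one and leave the differences unchanged.

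*Partly observed patient.* Ventilated Days 5-14, drug stopped Day 6, seen off the ventilator Days 15-20, no data Days 21-29. Observed free days: 4 (Days 1-4) + 6 (Days 15-20) = 10. Missing days: 9.

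| Reading | Days 15-20 | Days 21-29 | Ventilator-free days |
|---|---|---|---|
| Sentence 1, literal | ventilated | ventilated | 4 |
| Sentence 1, missing days only | free (observed) | ventilated | 4 + 6 = 10 |
| Sentence 2 | free (observed) | free | 4 + 6 + 9 = 19 |

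With imputation confined to missing days, the two sentences still differ by 19 - 10 = 9 days, or 9/65 = 0.14 day on the mean of an arm of 65 (Protocol Synopsis) per such patient.

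*Fully observed patient.* Ventilated Days 6-15, drug stopped Day 10, followed to Day 29. Observed: 29 - 10 = 19. Sentence 1, literal: ventilated Days 6-29, so 29 - 24 = 5. The difference is 14 days, or 14/65 = 0.22 day on the arm mean per such patient. If the rule fills only missing days, the difference is 0. It is also 0 if the patient stays ventilated to Day 29.

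**2. Time to response, only if censoring is at drug stop**

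The documents give no response or discontinuation rates, so every rate here is assumed:
- 25% of patients never respond; the others respond exponentially with a median of 9 days.
- Both arms have the same response distribution (true hazard ratio 1), with administrative censoring at 28 days.
- Drug stop is uniform on Days 2-9.
- The Cox model is unadjusted, with 600,000 patients per arm.

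In the main case the assigned stop probability is 36% in never-responders and 12% in responders on active drug, and 12% and 4% on placebo. That gives 0.25 x 36% + 0.75 x 12% = 18% v 6%. About a third of the responders' stop dates fall after their response and do not count, which leaves 15% v 5%.

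| Assumed stopping before response, active v placebo | Hazard ratio if censored at drug stop |
|---|---|
| 15% v 5%, partly related to prognosis | 1.06 |
| 5% v 15%, partly related | 0.94 |
| 10% v 5%, partly related | 1.03 |
| 10% v 10%, partly related | 1.00 |
| 15% v 5%, unrelated to prognosis | 1.00 |
| 15% v 5%, partly related; half of never-responders die and keep Day 29 censoring | 1.01 to 1.02 |
| 15% v 5%, only never-responders stop (extreme) | 1.16 |

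With full follow-up every case gives 1.00 within simulation error. In the first row about 5% of responses are discarded. With 65 per arm, the nominal 95% interval excludes 1 in 5.6% of runs, against 4.9% with full follow-up.

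A second model gives a shift of similar size. In it, 75% of continuing patients respond by Day 29 with no drug effect, and discontinuers have a 20% or 50% chance of responding in the 28 days after stopping. At 15% v 5%, full follow-up gives 0.85 or 0.91 and censoring at drug stop gives 0.93 or 0.95. The ratios are 0.93/0.85 = 1.09 and 0.95/0.91 = 1.04.

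**The case against.** The strongest reply is that these rules are incomplete rather than wrong.

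- **Section 6.6 concerns missing data.** Its heading says so, and it opens by stating that patients are followed after stopping drug. On that reading no recorded day is replaced. This stands for the fully observed patient, whose discrepancy disappears. It does not settle the partly observed patient, who still gets 10 or 19.
- **The two sentences name different quantities**, and only the second names ventilator-free days. That may be the intent. But ventilated and ventilator-free days are complements over the same calendar days, so Days 21-29 would be counted as both.
- **The last observed assessment most naturally means the last in the study.** Follow-up after drug stop needs the patient's agreement (Protocol 3.3.4.1), Protocol 7.3 leaves detail to the TSAP, and Protocol 7.2.3 is equally silent on loss to follow-up. Discharge counts as response, and its date is recorded (Protocol 5.1.3). For a patient who entered at grade 5, a 2-point improvement already means being out of hospital. This stands: on that reading the effect is nil or small.
- **Deaths are largely covered.** Score 10 for the remaining visits keeps those days out of the ventilator-free count, and the Day 29 rule for deaths is more specific than the general censoring rule.
- **SAP Section 10 is not in the copy reviewed** and could hold derivation detail. The body cites it for the logistic regression and Cochran-Mantel-Haenszel code.

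A reader might go further and infer that the SAP censors at drug stop and so biases the hazard ratio. The text does not say that; the bias needs that reading plus prognostic and unbalanced stopping. A reader might also infer that nearly every early stopper loses ventilator-free days, because all patients enter on oxygen (Protocol 3.3.2). Being on oxygen keeps the score below 7, so the oxygen part of sentence 1 does not lower that count.

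**Conclusion.** The point holds on the text: the rules are wrong as written, and the consequence is minor to moderate. SAP 6.6 gives two anchors and two opposite results for one identifiable type of patient, and its first sentence lacks the missing-data limit used in the rule before it. The example patient scores 10 or 19 ventilator-free days under the more charitable reading, and 4 if sentence 1 is taken literally. This assumes that 6.6 feeds the count, and it arises only when ventilation status changes between drug stop and the last assessment. How many patients would do so is unknown.

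Naming drug discontinuation as a censoring trigger sits badly with the declared estimand and goes beyond Protocol 7.2.3. Its effect ranges from none to a hazard ratio of about 1.06 at the assumed 15% v 5%, in either direction, and is 1.00 if stopping is balanced or unrelated to prognosis. These figures illustrate size; they do not predict it.

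The documents do not support a claim that the primary result is at risk. The rules are worded for day counts and time to response, not for the Day 29 status of the primary endpoint, and Protocol 7.1 plans no formal testing.

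**What to change.** **SAP 6.6.** Limit the imputation for early discontinuers to days with no recorded data, and use status at the last observed assessment as the single anchor in both sentences.

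**SAP 7.5.2, time to response.** Remove treatment discontinuation as a censoring trigger. Count responses observed after drug stop up to Day 29, deriving missing WHO grades from oxygen, ventilation and hospitalisation data, as 6.6 already allows from other sources. Censor before Day 29 only at withdrawal of consent or loss to follow-up.

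**Clarification only.** State that the death rules take precedence for a discontinuer who dies: Day 29 censoring for time to response, and score 10 for ventilator-free days.

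The cost is SAP wording and derivation code. No new data are needed, because footnote f already provides for daily ventilation and oxygen data in discontinuers still in hospital. The wording should be settled before treatment information is released under SAP Section 8.
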